- 1. **Screening:** To be obtained within 28 days prior to study entry.
- 2. **Informed Consent:** Must be obtained prior to undergoing any study-specific procedures.
- 3. **Medical/Oncologic History:** Includes history of disease process (eg, staging) (active or resolved) and concurrent illness. Includes prior treatments and any current medical treatments for any condition.
- 4. **Physical Examination:** Physical examinations (PEs) may be performed within 48 hours prior to a scheduled visit. A full physical examination is required at Screening and abbreviated PEs should be performed as appropriate at each visit where complete physical examinations are not required. For both full and abbreviated exams, patient should be assessed for evidence of bleeding (eg, bruising, petechiae, or hematomas). No need to repeat PE if baseline assessment is within 96 hours on Cycle 1 Day 1.
- 5. Baseline Signs & Symptoms: Patients will be asked about any signs and symptoms experienced within the 14 days prior to study entry.
- 6. **Vital Signs:** Includes temperature, sitting or semi-recumbent (same position must be used throughout the study and documented in source notes) blood pressure (BP), pulse rate (PR, to be recorded in the sitting position after 5 minutes of rest), and pulse oximetry (at rest and after exertion). On Day 1 of each cycle, vital signs should be measured prior to dosing (predose), BP, and PR will be repeated 1 hour after dosing. The time window for Vital Signs will match the allowable window for PK and ECGs.
- 7. ECOG Performance Status: Use Eastern Cooperative Oncology Group (ECOG) see Appendices.
- 8. **Hematology**: No need to repeat on Cycle 1 Day 1 (C1D1) if baseline assessment performed within 72 hours prior to that date. Assessments performed on Cycle 2 Day 1 (C2D1) and each subsequent cycle should be performed within 48 hours prior to dosing. See Assessments section for Laboratory Tests list.
- 9. **Blood Chemistry**: No need to repeat on C1D1 if baseline assessment performed within 7 days prior to that date (with the exception of serum creatinine which must be performed within 72 hours of C1D1). See Assessments section for Laboratory Tests list. Note that chemistries performed require serum phosphorus measurements.
- 10. Coagulation: No need to repeat on C1D1 if baseline assessment performed within 72 hours prior to that date. See Assessments section for Laboratory Tests list.
- 11. **Urinalysis**: Dipstick is acceptable at Screening, during trial conduct, and the End of Treatment visit. At Screening, if dipstick shows urine protein ++ or above, perform 24-hour urine protein test. No need to repeat on C1D1 if baseline assessment performed within 7 days prior to that date. See Assessments section for Laboratory Tests list.
- 12. **Viral Disease Screening:** Hepatitis B virus surface antigen (HBsAg), hepatitis B core antibody (anti HBc), (HbcAb), hepatitis B surface antibody (anti HBs), hepatitis C virus antibodies (HCVAb), and human immunodeficiency virus testing (HIV) to be conducted by local laboratory where required by local regulations or if warranted by patient history.
- 13. Contraceptive Check (frequency to match that of pregnancy tests): Male patients who are able to father children need to affirm that they meet the criteria for correct use of 2 of the selected methods of contraception. The Investigator or his or her designee will discuss with the patient the need to use 2 highly effective contraception methods consistently and correctly and document such conversation in the patient's chart. In addition, the Investigator or his or her designee will instruct the patient to call immediately if one or both selected contraception methods are discontinued, or if pregnancy is known or suspected in the patient's partner.
- 14. **Triplicate 12-Lead ECG:** The Screening ECG will be a single 12-lead ECG. ECGs will be collected at times specified in Pharmacokinetic, ECG, CCl Sampling Schedule for Part 2B.
- 15. **Echocardiogram:** Echo to be done once patient is confirmed to meet all other inclusion requirements, beginning cycle 3 Day 1 predose and every 2 cycles for 6 months, then every 3 cycles. A ±7 day window will be applied.
- 16. **Troponin I and BNP:** No need to repeat on C1D1 if baseline assessment performed within 7 days prior to that date. Will be performed per the SOA and will be repeated if abnormal and clinically significant.

Protocol Activity	Screening (≤28 days prior to	Active Treatment Phase†- One Cycle = 28 Cycles 1 & 2				Cycles 3+		End of Treatment/ Withdrawal ²³	Post-Treatme nt Follow-Up ²⁴		
Visit Identifier (Visit Window) ^a	enrollment)	Day 1	Day 2°	Day 7	Day 10 ^b	Day 15	Day 21°	Day 1	Day 7		

- 17. **Alk Phos Fractionation**: Obtain alkaline phosphatase (ALP) fractionation (bone, liver) per the SOA and as clinically indicated. With each ALP increase in AE grade level once at the grade level, fractionation will be obtained and an appropriate clinical evaluation will be conducted to determine the suitability of the patient continuation in the trial.
- 18. **Registration**: patient number and dose level allocation assigned by Pfizer Inc.
- 19. **Study Treatment**: PF-06952229 will be administered orally for 7 days on, 7 days off, during a 28 day cycle. Day 1 safety laboratory tests must be reviewed by the Investigator prior to dosing at the beginning of each cycle for dosing confirmation. For Part 2B mCRPC patients will receive PF-06952229 in combination with enzalutamide. Patients will self dose as described above, with the exception of doses that will be administered on site. Patients must maintain their original dosing schedule regardless of dose reductions or holds. Patients will be required to return all bottles of PF-06952229 as well as the completed patient diary for drug accountability. On days of scheduled clinic visits, morning (AM) dosing should be undertaken in the clinic (ie, not at home).
- 20. **Tumor Assessments**: Tumor assessments will include CT or MRI of chest, abdomen and pelvis, and MRI of the brain. If a brain MRI is medically contraindicated, a CT scan with contrast (unless contrast is medically contraindicated) may be performed, however the same modality should be used on an individual patient throughout the study. Other disease sites may be imaged if disease is suspected. Tumor assessments will be performed at Screening and every 8 weeks (±7 days) for the first year, then every 12 weeks (±7 days). Bone scans will be performed as medically indicated. Tc-99m bone scans (required for CRPC at baseline) will be performed at baseline if disease is suspected and on study as appropriate to follow disease. Patients who are found to have hemorrhage in other organs will discontinue treatment with PF-06952229 and enter the follow-up portion of the trial. Tumor assessments with continue until radiographically and/or clinically (ie, for photographed or palpable lesions) documented PD as per RECIST v.1.1, study treatment discontinuation (for patients continuing treatment beyond RECIST defined disease progression), initiation of new anticancer therapy or discontinuation of patient from overall study participation (eg, death, patient's request, lost to follow-up), whichever occurs first. Given the exploratory nature of the study, confirmation of response (complete response (CR)/partial response (PR)) is preferred (see RECIST version 1.1). Tumor assessments should be repeated at the end of study visit if more than 6 weeks have passed since the last evaluation. Patients should have a confirmatory scan for PD and can remain on trial if they are receiving clinical benefit upon discussion with investigator and sponsor MD. Tumor assessments should be fixed according to the calendar, regardless of treatment delays. FDG-PET will be performed per standard of care.

Bone Scans for mCRPC: 99mTc-methylene diphosphonate radionuclide bone scintigraphy should be performed every 8 weeks for first 24 weeks, then every 12 weeks (up to 2 years), then every 16 to 24 weeks (±14 days). Changes in lesions that are considered metastatic on bone scintigraphy should be followed and assessed serially using a bone scan assessment form (see Appendices).

Prostate specific antigen (PSA) assessment to be performed on Screening (for historical progression per Prostate working Group 2), C1D1 (-14 days) and Day 1 of Cycle 4, 7, 10 and every 3rd cycle thereafter as well as the End of Treatment visit. Please see Appendix for Prostate Cancer Working Group 2 (PCWG2)- Soft Tissue Response Criteria.

Gleason Score should be collected at diagnosis.

Protocol Activity	Screening		Active	Treatme	ent Phas	e†- One (Cycle = 2	28 days		End of	Post-Treatme
	(≤28 days prior to enrollment)	Cycles 1 & 2				Cycles 3+		Treatment/ Withdrawal ²³	nt Follow-Up ²⁴		
Visit Identifier (Visit Window) ^a		Day 1	Day 2°	Day 7	Day 10 ^b	Day 15	Day 21°	Day 1	Day 7		

- 21. Adverse Event (AE) Assessments: AEs should be documented and recorded at each visit using the National Cancer Institute Common Terminology Criteria for Adverse Events (NCI CTCAE) version 5.0. The time period for actively eliciting and collecting AEs and SAEs ("active collection period") for each patient begins from the time the patient provides informed consent through and including a minimum of 28 calendar days after the last investigational product administration. If the patient begins a new anticancer therapy, the period for recording non-serious AEs on the CRF ends at the time the new treatment is started. However, any SAEs occurring during the active collection period must still be reported to Pfizer Safety and recorded on the CRF, irrespective of any intervening treatment.
- 22. Concomitant Treatments: All concomitant medications and NonDrug Supportive Interventions should be recorded on the CRF including supportive care drugs, eg, anti-emetic treatment and prophylaxis, radiotherapy on study is permitted (eg, skeletal administration for CRPC), drugs used to treat adverse events or chronic diseases, and non-drug supportive interventions (eg, infusions).
- 23. **End of Treatment/Withdrawal:** Visit to be performed as soon as possible but no later than 4 weeks from the last dose of investigational products and prior to initiation of any new anti-tumor therapy. Obtain assessments if not completed during the previous 4 weeks on study (or within the previous 8 weeks or 12 weeks as applicable for disease assessments).
- 24. **Post Treatment Follow-Up:** At least 28 days, and no more than 35 days after discontinuation of treatment patients will return to undergo review of concomitant medications, ECOG, abbreviated physical exam, and assessment for resolution of any treatment related toxicity. Patients continuing to experience toxicity at this point following discontinuation of treatment will continue to be followed at least every 4 weeks until resolution or determination, in the clinical judgment of the investigator, that no further improvement is expected.
- 25. **Survival Follow-Up:** Subsequent to the follow-up period, overall survival (OS) follow-up will be conducted by telephone every 8 weeks (±7 days) until end of the entire study (2 years after last patient first treatment). If the patient is seen in the clinic during the window of time that a scheduled telephone call is to be made to collect survival data, then the clinic visit may replace the survival telephone call.

Pharmacokinetic, ECG, CCl Sampling Schedule for Part 2B - Combination Dose Expansion

Visit Identifier		Screen			Cycle 1				C	ycle 2		Cycle ≥3	EOT
Study Day			Day 1	Day 2**	Day 7	Day 15	Day 21**	Day 1	Day 2**	Day 7	Day 10 (-24 hrs)	Day 7	
Dose of PF-06952	2229 in clinic ¹		X*	X	X	X	X	X*	X	X		X	
				Pl	narmacok	inetics (P	K)						
Predose (if dosing	g day)		N, E	N	N, E	N	N,E	N, E	N	N	N	N	N
First 8	0.5 hours (±5 min)		N				N	N					
Patients only (min)	1 hour (±10 min)		N				N	N					
2 hours (±15 min))		N		N	N	N	N		N			
First 8 Patients	4 hours (±25 min)		N				N	N					
only (min)	6 hours (±40 min)		N				N	N					
	12 hours (-180 min)		N				N	N					
	,				12-Lea	ıd ECG ²							
0		X	X	X	X	X	X			X		X	X
2 hours (±15 min))		X		X	X	X						
					CCI								
							_	_		_	_		
			'					•		•	'		

Visit Identifier	Screen			Cycle 1				C	cycle 2		Cycle ≥3	EOT
Study Day		Day 1	Day	Day 7	Day 15	Day	Day 1	Day	Day 7	Day 10	Day 7	
			2**			21**		2**		(-24 hrs)		
Abbreviation: PK = pharmacokinetic; CC		; EO	$\Gamma = End o$	f Treatme	nt; N=PF-0	6952229	; E=Enzalı	ıtamide; (

^{*} On Day 1 of Cycle 1 and Cycle 2 only a single dose of PF-06952229 to be given to evaluate PF-06952229 PK sampling up to 24 hr time point (i.e. pre-dose on Day 2 of Cycle 1 and Cycle 2).

- 1. **Dose of PF-06952229 in Clinic:** On days of scheduled clinic visits, morning (AM) dosing should be undertaken in the clinic (ie, not at home).
- 2. **Triplicate 12-Lead ECG:** The Screening ECG will be a single 12-lead ECG. At all other times, at each time point, 3 consecutive 12-lead ECGs (triplicate) will be performed approximately 2 minutes apart to determine mean QTcF interval. All 12-lead ECGs should be confirmed by a qualified person at the institution. When coinciding with blood sample draws for pharmacokinetics (PK), ECG assessment should preferably be performed prior to blood sample collection, such that the blood sample is collected at the nominal time. If the mean QTcF is prolonged (≥45 msec from the baseline or >500 msec), the ECGs should be re-evaluated by a qualified person at the institution for confirmation. Additional triplicate ECGs may be performed as clinically indicated.

^{**} Day 2 and Day 21 visit for first 8 subjects (min).

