Part 1A is a sequential single-agent dose-escalation conducted in patients with advanced or metastatic solid tumors who have failed standard-of-care treatment or for whom no standard-of-care exists. Successive cohorts of patients are to receive escalating doses of PF-06952229 on an outpatient basis starting from 20 mg BID, which is based on non-clinical data. Nine candidate dose levels are planned using an Accelerated Titration Design (ATD) until reaching 250 mg BID, after which the design will revert to modified target probability interval (mTPI). The highest tested dose will not exceed 800 mg BID. If an MTD is not observed during the 28-day safety window, additional dose levels may be considered based on PK, safety, tolerability, CCI assessments. Based on PK and safety, additional patients can be added to a dose lower than the MTD and also may be moved forward to monotherapy expansion.

Part 1B is a dose-escalation of PF-06952229 in the combination of enzalutamide conducted in patients who were previously treated with metastatic castration-resistant prostate cancer (mCRPC). The starting dose of PF-06952229 will be the MTD or maximum administered dose (MAD) of Part 1A. Based on evolving PK, PD, and safety profiles, assessed in Part 1A, Part 1B may commence before reaching the MTD, and will follow an mTPI design. The maximum PF-06952229 dose for the combination escalation may be higher than the monotherapy MTD due to the potential DDI between enzalutamide and PF-06952229, but not higher than 800 mg BID.

Part 2A and Part 2B are expansion cohorts for monotherapy and combination therapy, respectively, in patients with previously treated mCRPC.

To assess baseline TGF β related biomarker signatures that may correlate with clinical efficacy, all patients enrolled in Part 1 will be required to provide a recent archival tumor sample or to undergo a fresh pre-treatment biopsy if archival samples are unavailable prior to trial treatment.

Part 2 patients are required to provide either a recent archival tumor biopsy or, for all patients in Part 2A and from approximately 10 patients in Part 2B, mandatory de novo biopsies. Mandatory de novo pre-treatment and on-treatment tumor biopsies may not be required where it is determined that it is not medically feasible (such as constituting unacceptable medical risks). However, this would require agreement of Investigator and Sponsor.

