- 24. **Post Treatment Follow-Up:** At least 28 days, and no more than 35 days after discontinuation of treatment patients will return to undergo review of concomitant medications, ECOG, abbreviated physical exam, and assessment for resolution of any treatment related toxicity. Patients continuing to experience toxicity at this point following discontinuation of treatment will continue to be followed at least every 4 weeks until resolution or determination, in the clinical judgment of the investigator, that no further improvement is expected.
- 25. **Survival Follow-Up:** Subsequent to the follow-up period, overall survival (OS) follow-up will be conducted by telephone every 8 weeks (±7 days) until end of the entire study (2 years after last patient first treatment). If the patient is seen in the clinic during the window of time that a scheduled telephone call is to be made to collect survival data, then the clinic visit may replace the survival telephone call.

Pharmacokinetic, ECG, CCI Sampling Schedule for Part 1B - Combination Dose Escalation with Enzalutamide

Visit Identifier	Screen			Cycle 1				Cyc	le 2		Cycle ≥3	EOT
Study Day		Day 1	Day 2	Day 7	Day 15	Day 21	Day 1	Day 2	Day 7	Day 10 (-24hrs)	Day 7	
Dose of PF-06952229 in clinic ¹		X*	X	X	X	X	X*	X	X		X	
					Pharmacokin	netics (PK)		•	•		•	
Predose (if dosing day)		N, E	N	N, E	N	N, E	N, E	N	N	N	N	N
0.5 hours (±5 min)		N				N	N					
1 hour (±10 min)		N				N	N					
2 hours (±15 min)		N				N	N					
4 hours (±25 min)		N				N	N					
6 hours (±40 min)		N				N	N					
12 hours (-180 min)		N				N	N					
					12-Lead	ECG ²						
0	X	X	X	X	X	X			X		X	X
2 hours (±15 min)		X				X						
4 hours (±25 min)		X				X						
					CCI							
							_					
						'						

Visit Identifier	Screen			Cycle 1				Cyc	le 2		Cycle ≥3	EOT
Study Day		Day 1	Day 2	Day 7	Day 15	Day 21	Day 1	Day 2	Day 7	Day 10 (-24hrs)	Day 7	
CCI										(2 m/s)		
Abbreviation: PK = ph	armacokinetic	CCI		; EOT = End	of Treatment	; N=PF-0695	52229; E=Enzal	utamide; CC				

^{*} On Day 1 of Cycle 1 and Cycle 2 only a single dose of PF-06952229 to be given to evaluate PF-06952229 PK sampling up to 24 hr time point (ie, pre-dose on Day 2 of Cycle 1 and Cycle 2)

- 1. **Dose of PF-06952229 in Clinic:** On days of scheduled clinic visits, morning (AM) dosing should be undertaken in the clinic (ie, not at home).

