1.2.4. Nonclinical Pharmacokinetics

The nonclinical pharmacokinetic/toxicokinetic, absorption, distribution, metabolism, and excretion (ADME) properties of PF-06952229 have been evaluated in vitro and in vivo to support nonclinical safety evaluations and to assess the potential relevance to humans. The oral pharmacokinetics (PK) of PF-06952229 in nonclinical species indicated moderate to high oral absorption and bioavailability. Systemic exposure increased with dose in pivotal toxicity studies in rats and monkeys. PF-06952229 was highly bound to plasma proteins across species and, in general, demonstrated limited distribution into red blood cells. In vitro studies suggest PF-06952229 may be a substrate for the efflux transporters such as human P-glycoprotein (P-gp) and breast cancer resistance protein (BCRP). The moderate to high bioavailability observed in nonclinical species indicate that oral absorption was not limited by these efflux transporters.

The primary clearance mechanism of PF-06952229 was cytochrome P450 (CYP) 3A4-mediated metabolism ($f_m \sim 0.9$), with limited to no renal or biliary excretion. Consequently, significant changes in PF-06952229 exposure are anticipated following co-administration with strong CYP3A4 inhibitors or inducers. Following co-administration of PF-06952229 with enzalutamide (a strong inducer of CYP3A) a 70% decrease (AUC_R ~ 0.3) in PF-06952229 AUC was predicted. No unique human metabolites were observed in vitro compared to metabolite profiling in rat.

Assessments based on in vitro drug-drug interaction (DDI) studies and the predicted systemic exposure in humans following the projected efficacious dose indicate a low potential for DDI due to PF-06952229-mediated inhibition of CYP 1A2, 2B6, 2C8, 2C9, 2C19, and 2D6 or uridine diphosphate-glucuronosyltransferase (UGT) 1A4, 1A6, 1A9, 2B7 and 2B15. However, PF-06952229 may have the potential to inhibit CYP3A (time-dependent) and UGT1A1 (reversible) at concentrations associated with the projected efficacious dose. The

potential for DDI due to PF-06952229-mediated inhibition of organic anion-transporting polypeptides (OATP) 1B1 and 1B3, organic anion transporter (OAT) 1 and OAT3, organic cation transporter (OCT) 2, multi-antimicrobial extrusion protein (MATE) 1, and MATE2K is low. However, PF-06952229 has the potential to inhibit intestinal P-glycoprotein (P-gp) and breast cancer resistance protein (BCRP) at the projected efficacious dose.

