3.1.1.5. Part 1B – PF-06952229 in Combination With Enzalutamide in mCRPC

Part 1B is a dose-escalation of PF-06952229 in combination with enzalutamide conducted in patients who were previously treated for mCRPC. The starting dose of PF-06952229 will be based on safety, PK, and potential efficacy, but will not exceed the MTD or MAD of Part 1A. Because of the potential DDI between enzalutamide and PF-06952229, the maximum PF-06952229 dose for the combination may be higher than the monotherapy MTD, but not

higher than 800 mg BID. In addition to safety and tolerability, PF-06952229 PK exposure data may be reviewed for informed dose escalation. Based on evolving PK, PD and safety profiles, assessed in Part 1A, Part 1B may commence before reaching the MTD in Part 1A, and will follow an mTPI design as described in Section 3.1.1.4.

Enzalutamide (a CYP3A4 inducer) is predicted to decrease the PK of PF-06952229 (a CYP3A4 substrate) by 70% (Section 1.2.4). PF-06952229 is not expected to impact the PK of enzalutamide, therefore a fixed dose of enzalutamide is 160 mg QD, administered on a continuous basis. Dose modifications to enzalutamide will not be allowed during the DLT evaluation period.

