5.4. Administration

5.4.1. PF-06952229

Patients will swallow the investigational product whole, and will not manipulate or chew the investigational product prior to swallowing.

PF-06952229 will be administered twice a day (BID) on an intermittent basis (7 days on/7 days off). A cycle is defined as 28 days, regardless of missed doses or dose delays.

PF-06952229 will be administered orally on an empty stomach without adjustment for body size at every cycle, CCI

No food or liquids other than water will be consumed for 2 hours before and 1 hour following each dose throughout the study.

Patients should be instructed to take their medication at approximately the same time each day (approximately every 12 hours) and to not take more than the prescribed dose at any time.

On days of scheduled clinic visits (see the Schedule of Activities for Parts 1 and 2), morning (AM) dosing of PF-06952229 should be undertaken in the clinic (ie, not at home). On those days where the morning dose of PF-06952229 is held due to a specific study visit, the second BID dosing should be taken no sooner than 8 hours, and no later than 16 hours post the first BID dosing (allowable treatment window ±4 hours). On Day 1 of Cycle 1 and Cycle 2 in Part 1B and Part 2B, only a single dose of PF-06952229 to be given to evaluate PF-06952229 PK sampling up to 24 hr time point (ie, pre-dose on Day 2 of Cycle 1 and Cycle 2).

If a patient misses a dose by more than 4 hours, he/she must be instructed not to "make it up" but to resume the subsequent dose as prescribed.

If a patient vomits 1 hour or more after taking a dose, he/she must be instructed not to "make it up" but to resume subsequent doses and site should discuss dosing with sponsor.

If a patient inadvertently takes 1 extra dose during a day, the patient should not take the next dose of PF-06952229.

[figure not shown]
In Part 1B and Part 2B of the study, PF-06952229 is given in combination with enzalutamide in patients with mCRPC. After an appropriate dose of PF-06952229 is selected in the combination dose escalation cohort (Part 1B), the combination will be tested in a dose expansion cohort (Part 2B) of enzalutamide and PF-06952229.

A dosing diary will be given to the patient to support at-home dosing.

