5.7.1. Proton-Pump Inhibitors

Acid reducing agents (ARAs) may decrease PF-06952229 absorption and exposure. The potential impact to absorption and exposure may be the greatest with proton pump inhibitors (PPIs). When possible patients who are currently taking PPIs should be switched to antacids

or H2-Receptor antagonists (see below) at least 14 days prior to Cycle 1 Day 1 and continue with these alternative ARAs throughout the study.

In Part 1A, Part 1B, and Part 2B, if the patient starts the study treatment period currently taking a PPI, the dose and frequency should be recorded in the appropriate CRF page and the patient should maintain this treatment until after Cycle 2 Day 1 visit, to allow for more accurate estimation of the impact of enzalutamide (Part 1B, and Part 2B) on PF-06952229 exposure. If the patient stops or alters treatment with PPI during this period, this should be recorded in the CRF.

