9.4. Analysis of Pharmacokinetics CCl

9.4.1. Analysis of Pharmacokinetics

9.4.1.1. Single-Dose and Steady-State PF-06952229 Pharmacokinetic Analysis

Plasma PK parameters including the maximum plasma concentration (C_{max}), time to maximum plasma concentration (T_{max}), and area under the plasma concentration versus time curve (AUC_{last}) for PF-06952229 will be estimated using noncompartmental analysis. If data permit or if considered appropriate, area under the plasma concentration versus time curve from time 0 extrapolated to infinity (AUC_{inf}), terminal elimination half-life ($t_{1/2}$), apparent oral plasma clearance (CL/F), apparent volume of distribution (V_{ss} /F or V_z /F), accumulation ratio (R_{ac}) and linearity ratio (R_{ss}) will be also estimated. The single-dose and steady-state PK parameters will be summarized descriptively (n, mean, standard deviation, coefficient of variation [CV], median, minimum, maximum, geometric mean and its associated CV) by dose, cycle and day.

For PF-06952229 concentrations, concentrations will be summarized descriptively (n, mean, standard deviation, CV, median, minimum, maximum, geometric mean and its associated

CV) by dose, cycle, day and nominal time. Individual patient and median profiles of the concentration-time data will be plotted by dose, cycle and day (single dose and steady state) using nominal times. Individual and median profiles will be presented on both linear-linear and log-linear scales.

Dose normalized AUC_{last} and C_{max} will be plotted against dose (using a logarithmic scale) by cycle and day. These plots will include individual patient values and the geometric means for each dose. These plots will be used to help understand the relationship between the PK parameters and dose.

The observed accumulation ratio and the linearity ratio will be summarized descriptively. Each will be analyzed after natural log transformation using a one-way analysis of variance (ANOVA) with a single term for dose. The means and 90% confidence intervals (CIs) obtained from the model will be back-transformed to provide means and 90% CIs for the accumulation and linearity ratios for each dose.

Trough concentrations will be plotted for each dose using a box-whisker plot by cycle and day within cycle in order to assess the attainment of steady state.

Urine PK parameters (Ae%, CL_R) for PF-06952229 will also be estimated and summarized.

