6.3.2. Pharmacokinetics Analyses

The concentration-time data of PF-06952229 will be summarized by descriptive statistics (n, mean, standard deviation, coefficient of variation, median, minimum, maximum, and geometric mean) according to dosing cohort and time for each part of the study. In addition, the concentration-time data from Part 2 dose expansion will also be summarized by descriptive statistics according to tumor type.

The actual time of sample collection will be used in PK parameter calculation. In the event that the actual sampling time is not available, the nominal time may be used if there is no evidence that the actual sampling time deviates substantially from the nominal time.

Presentation of PF- PF-06952229 concentration-time data

The concentration-time data of PF-06952229 will be presented as below:

- a listing of all concentrations by cohort, subject ID and nominal time. The concentration listing will also include the actual times. Deviations from the nominal time will be given in a separate listing.
- a summary of concentrations by cohort and nominal time, where the summary statistics will include n, mean, standard deviation, median, coefficient of variation (cv), minimum, maximum and the number of concentrations above the lower limit of quantification.
- for the concentration-time data after the 1st (C1D1) and 7th dose (C1D7), median concentration-time plots (on both linear and semi-log scales) against nominal time postdose by cohort (all cohorts on the same plot per scale, based on the summary of concentrations by cohort and time postdose).

For drug concentration summary statistics, median and mean plots by sampling time, the nominal PK sampling time will be used; for individual subject plots by time, the actual PK sampling time will be used, with the pre-dose time set to zero.

Calculation of PF-06952229 PK parameters

For patients enrolled in the dose escalation stage of the study, the individual concentration-time data of PF-06952229 during Cycle 1 and Cycle 2 will be analyzed separately by non-compartmental methods to estimate the PK parameters. The PK parameters estimated will include C_{max} , T_{max} , and AUC_{last} (AUC_{tau} at steady state). If data permit or if considered appropriate, $t_{1/2}$, CL/F , V_d/F (or V_{ss}/F at steady state), and accumulation ratio (R_{ac}) will also be estimated. The PK parameters will be summarized descriptively by dose level and cycle.

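### Parts 1B and 2B collect matched single-dose profiles on C1D1 and C2D1, but the readable PK analysis text specifies no within-patient C2D1/C1D1 ratio for the effect of enzalutamide

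*Protocol*

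**What the plan says.** **Design.** The footnote to the PK sampling schedules for Parts 1B and 2B reads "On Day 1 of Cycle 1 and Cycle 2 only a single dose of PF-06952229 to be given to evaluate PF-06952229 PK sampling" up to the 24-hour point, which is the Day 2 pre-dose sample. Protocol 5.4.1 repeats it: "On Day 1 of Cycle 1 and Cycle 2 in Part 1B and Part 2B, only a single dose of PF-06952229 to be given". Both days have samples pre-dose and at 0.5, 1, 2, 4, 6 and 12 h. In Part 2B the full profile is for a minimum of the first 8 patients. Protocol 5.7.1 asks patients who enter on a proton-pump inhibitor to stay on it until after C2D1, "to allow for more accurate estimation of the impact of enzalutamide (Part 1B, and Part 2B) on PF-06952229 exposure".

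**Use of the interaction.** Protocol 1.2.4 reports that with enzalutamide "a 70% decrease (AUC_R ~ 0.3) in PF-06952229 AUC was predicted". The Study Overview says the maximum combination dose "may be higher than the monotherapy MTD due to the potential DDI between enzalutamide and PF-06952229", with a cap of 800 mg BID. Protocol 3.1.1.5 adds that "PF-06952229 PK exposure data may be reviewed for informed dose escalation" and names no estimator.

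**Analysis.** Protocol 9.4.1.1: "The single-dose and steady-state PK parameters will be summarized descriptively", by dose, cycle and day. The only ratios it models are accumulation and linearity. SAP 6.3.2 says that in dose-escalation patients the concentration data "during Cycle 1 and Cycle 2 will be analyzed separately by non-compartmental methods", with parameters then summarised by dose level and cycle. For Part 2 the SAP gives concentration summaries and trough concentrations. Single- and multiple-dose parameters in at least 8 patients are nevertheless a Part 2B secondary endpoint (Protocol Section 2).

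**The concern.** The schedule looks built for a within-patient comparison: the same patient, the same single-dose condition, the same sampling times and a stable acid-reducing background, once at the start of treatment and once after a cycle with enzalutamide. Section 5.7.1 states the purpose. The analysis text that can be read does not deliver that estimate. It describes each cycle within each dose level, so the comparison is spread over small cohorts (2-4 patients each, Protocol 3.3) and the pairing is not used.

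The accumulation ratio does not fill the gap. In Part 1B it would set the C1D21 profile against C1D1, which mixes accumulation with any induction by enzalutamide, and it leaves C2D1 unused. The SAP also plans concentration plots for C1D1 and C1D7, but Part 1B takes only a pre-dose sample on C1D7. Its rich profiles fall on C1D1, C1D21 and C2D1, which suggests that the SAP text was not adapted to this schedule.

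At stake is the check on the predicted AUC ratio of about 0.3. That interaction is the reason given for allowing combination doses above the monotherapy MTD, and it is one of two reasons given in Protocol 3.4 for a different combination RP2D.

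**Working it through.** **1. The plan's own figures.** A 70% decrease is a ratio of 1 - 0.70 = 0.30, so the two forms agree. The prediction itself cannot be rebuilt, because its induction inputs are not given. Protocol 1.2.4 predicts CL 5 mL/min/kg and Vss 3 L/kg: half-life = ln 2 × 3000 / 5 = 416 min = 6.9 h, matching the stated 7 h.

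**2. Are C1D1 and C2D1 comparable single-dose profiles?** From the last Cycle 1 dose (evening of Day 21) to the C2D1 morning dose is about 7.5 days = 180 h, or 180 / 7 ≈ 26 half-lives, so carry-over of drug is negligible. Sampling to 24 h covers 1 - 2^(-24/7) = 91% of AUCinf; 12 h would cover 70%. On the predicted half-life, the two days are suited to a direct comparison.

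**3. Precision, paired against separate summaries at the same n.** The documents give no CV for PF-06952229 AUC. Assumed: true ratio 0.30, within-patient CV 30%, between-patient CV 60%.

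- s_w = √ln(1 + 0.30²) = 0.294; s_b = √ln(1 + 0.60²) = 0.555; √(s_w² + s_b²) = 0.627.
- Paired: SE = s_w·√(2/n), t on n - 1 df.
- Cycles treated as independent: SE = 0.627·√(2/n), t on 2n - 2 df.
- 90% limits = 0.30·exp(± t·SE).

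| n | Paired t × SE | Paired 90% CI | Unpaired t × SE | Unpaired 90% CI |
|---|---|---|---|---|
| 4 | 2.353 × 0.208 | 0.18-0.49 | 1.943 × 0.444 | 0.13-0.71 |
| 8 | 1.895 × 0.147 | 0.23-0.40 | 1.761 × 0.314 | 0.17-0.52 |
| 20 | 1.729 × 0.093 | 0.26-0.35 | 1.686 × 0.198 | 0.21-0.42 |

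Here n = 4 is the largest cohort size named in Protocol 3.3, n = 8 the Part 2B minimum, and n = 20 the planned Part 1B total if every patient has both profiles.

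**4. Range of the assumption (n = 8).** With CVs of 20% and 40% (s_w 0.198, s_b 0.385): paired 0.25-0.36, unpaired 0.20-0.44. With CVs of 40% and 80% (s_w 0.385, s_b 0.703): paired 0.21-0.43, unpaired 0.15-0.61. Pairing is narrower in both. Pooling over doses is a second, separate gain, seen by reading down the table.

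**5. Is C1D1 a clean baseline?** This is not assured. The first exclusion criterion in Protocol 4.2 bars enzalutamide within 24 days for Part 1B. Criterion 31 with Appendix 9, which lists enzalutamide as an inducer, uses 10 days or 5 half-lives, whichever is longer. The text does not clearly give the first enzalutamide day. An enzalutamide sample is scheduled pre-dose on C1D1, so affected patients can be identified.

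**The case against.** **Redaction.** Material is blacked out directly after Protocol 9.4.1.1, in the Part 1B objectives, and in the SAP between 6.3.2 and 6.6. Enzalutamide samples and the Part 1A meal are scheduled but have no readable analysis either, so the public PK text is plainly incomplete. A reader might infer that the trial will not estimate the interaction within patient. The documents do not support that; they show only that the readable sections specify no such estimate. This part of the objection stands in full.

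**Nothing is lost.** Profile-by-profile non-compartmental analysis is needed for any ratio, concentrations are listed by subject, dose-normalised AUC and Cmax are plotted with individual values, and SAP 5.3 allows added exploratory analyses. So the ratio could be computed later. That is true, but an estimate with a purpose stated in the protocol should not depend on a later addition.

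**Cross-part comparison.** A reader might think Part 1A cannot serve as a reference because a meal is given on C2D1. That does not hold: C1D1 and C1D7 in Part 1A carry no meal and have rich sampling, and Part 2A has no meal row. A cross-part comparison is possible. It is less efficient than pairing because between-patient variation enters it.

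**Exaggerated gain.** Setting 20 paired patients against 4 unpaired would mix pooling with pairing. The same-n figures above avoid this.

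**Phase 1.** SAP 5.1 has no hypotheses, and no readable objective names the interaction. This limits the weight of the point, not the case for an inexpensive estimate.

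**Conclusion.** The point holds in limited form. Matched single-dose profiles to 24 h are collected on C1D1 and C2D1, and a purpose of estimating enzalutamide's effect is stated. The readable PK analyses in both documents specify no within-patient ratio. For Part 2B the gap is wider, because the readable SAP text does not cover the parameters that are its secondary endpoint.

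The gain from pairing is moderate: at n = 8, 0.23-0.40 against 0.17-0.52; at n = 20, 0.26-0.35 against 0.21-0.42. These figures rest on assumed CVs, a true ratio of 0.30 and both profiles being available in every patient counted. Pooling also assumes a similar ratio across dose levels. The ratio attributes the whole change between the two days to enzalutamide, which depends on the C1D1 baseline being free of it.

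Two stronger readings are not supported. The interaction is not the only reason for a different combination RP2D: Protocol 3.4 also names overlapping toxicity. Nor does the gap justify making the ratio a condition for opening a dose cohort. That would be a dose-escalation rule, which is outside this review, and the documents already govern escalation through DLTs and a dose cap.

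**What to change.** Unless a redacted section already does so, add to SAP 6.3.2, for Part 1B and the Part 2B PK subset:

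- non-compartmental parameters on C1D1 and C2D1;
- the within-patient log ratio C2D1/C1D1 of dose-normalised AUC (0-24 h, and AUCinf where estimable) and Cmax, pooled over dose levels, reported as a geometric mean ratio with 90% CI;
- a sensitivity analysis excluding patients with measurable enzalutamide in the C1D1 pre-dose sample.

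Ask the sponsor to reconcile the prior-enzalutamide limits in Protocol 4.2 (the Part 1B criterion against criterion 31 and Appendix 9) and to state the first enzalutamide day. The sponsor should also reconcile the allowance for doses above the monotherapy MTD (Protocol 3.1 and 3.1.1.5) with C1D1 dosing that may precede any enzalutamide effect. No dosing or escalation rule is proposed here.

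Cost: one extra PK table. No new samples, visits or change to dosing.
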